#### 15. Exclusion criteria

1. Chronic kidney disease KDIGO stage 4, 5, or 5D.
2. Next of kin unwilling or patient unwilling to participate.
3. Patients with a life expectancy of fewer than 72 hours according to the attending physician criteria.
4. Patients older than 75 years.
5. Patients with SOFA > 11.
6. Patients with severe liver failure.

#### 16. Statistical analysis

Descriptive statistics will be used with measures of central tendency and dispersion of the data according to their distribution. The distribution of the variables will be analyzed with the Kolmogorov-Smirnov "Z" test. For categorical variables, frequencies and percentages will be used. For continuous variables with normal distribution, the mean and standard deviation will be shown. In contrast, the median and interquartile range will be used for continuous variables with an abnormal distribution.

The Student's t-test will be used to compare continuous variables between the two groups, in case of a normal distribution. The Mann-Whitney U-test will be performed for groups with an abnormal distribution. The analysis of data inside the same group at different time intervals (baseline vs 72 h) will be carried out using the Student's t-test, Wilcoxon sum of ranks, or McNemar's test, as appropriate.

Multivariate analysis for mortality will be performed using Cox proportional hazards, adjusted for the baseline SOFA score. Statistical analysis and graphs will be obtained using SPSS 19.0 software (Chicago, IL) and Graphpad Prism 5 software (San Diego, Ca), respectively. A p-value <0.05 will be considered significant. An intention-to-treat analysis will be pursued.

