1. Title

A randomized, open-label, controlled trial to evaluate efficacy and safety of a highly selective semipermeable membrane (AN-69 Oxiris) in comparison with a semi selective semipermeable membrane (standard AN-69) in COVID-19 associated acute kidney injury: oXAKI-COV study.

2. Number and version

V1.04, October 17th, 2020

3. Type of research

Randomized controlled trial

2-group design

Follow-up study

Prospective

Interventional

Multicentric

Open-label

4. Research group

5. Participating institutions

INCMNSZ. Research study workplace and place of treatment administration.

6. Financial support: neither grants nor payment for researches.

7. Abstract

Title: Randomized, open-label, controlled trial to evaluate efficacy and safety of a highly selective semipermeable membrane (AN69-Oxiris) in comparison with a selective semipermeable membrane ( standard AN69) in COVID-19 associated acute kidney injury: oXAKI-COV study

Rationale: Acute kidney injury (AKI) in critically ill mechanically ventilated patients with COVID-19 disease, is present in up to 30% of this group and more than 50% of them will need renal replacement therapy in the form of continuous renal replacement therapy (CRRT). Acute kidney injury in this context seems to be a marker of multiorgan dysfunction and it produces increased mortality in this population. There is a vast amount of mechanisms that lead to AKI in critically ill patients with COVID-19; however, the cytokine storm could be the strongest mechanism implicated in AKI development in individuals with continuous renal replacement therapy requirements. Therefore, blocking or reducing the cytokine storm is thought to be a therapeutic target.

Highly selective semipermeable membranes (AN69-Oxiris) have been shown able to adsorb endotoxins and to eliminate inflammatory cytokines, thus representing a valuable therapeutic option in this infection.

Objective: Change in norepinephrine requirement by at least 0.1 micrograms / kg / min to maintain similar MAP after initiation of CRRT with Oxiris membrane compared to standard AN69 membrane. MAP measurements will be performed hourly and norepinephrine requirement will be recorded at that time.

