## 9. Hypothesis

Research question: In critically ill patients with COVID-19 disease and AKI requiring CRRT, is the AN69-Oxiris membrane of greater benefit to sustain MAP a lower vasopressor dose in comparison with a conventional AN69 standard membrane, after 72 hours of treatment?

Alternative hypothesis: The use of the AN69-Oxiris membrane will decrease vasopressor requirement in at least 0.1 micrograms/kilogram/minute to sustain a stable MAP in contrast with the usage of AN69 standard membrane, in critically ill patients with COVID-19 and AKI requiring CRRT after 72 h of treatment.

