## 10. Goals

Primary goal: Change in norepinephrine requirement by at least 0.1 micrograms / kg / min to maintain similar MAP after initiation of CRRT with Oxiris membrane compared to standard AN69 membrane. MAP measurements will be performed hourly and norepinephrine requirement will be recorded at that time.

Exploratory goals:

- Effectiveness of the AN69-Oxiris membrane in reducing interleukin serum levels (IL 6, IL 10, and TNF alpha).

Serum will be taken every 8 hours for its measurement by ELISA method.

- To establish the safety (the same risk infection and bleeding) of using the AN69- Oxiris membrane in patients with AKI and COVID-19 infection who require CRRT.

Gross bleeding events (gastrointestinal or urinary) as well as catheter-associated infection events (criteria according to IDSA) will be recorded.

- Length of stay in UCI among patients who used AN69-Oxiris membrane in compared to the use of a conventional membrane (standard AN-69) in critically ill patients with COVID-19 associated AKI and CRRT requirement.

- To investigate the effect of AN69-Oxiris in reducing 28-day mortality in contrast compared with the effect of a conventional membrane in this population.

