## 11. Methods

Study design: A randomized, multicentric, open-label, controlled trial

Study population: Critically ill patients on mechanical ventilation with AKI and CRRT requirements admitted with COVID-19 disease in any of the two participant institutions.

Participating institutions: INCMNSZ , INER

Timing: October 02th, 2020 to December 30th, 2021.

Interventions: patients meeting inclusion criteria and accepting to participate in this study with informed consent (or legal representative via phone call giving the pandemic lockdown), will be randomized to be treated with CRRT using the AN-69 Oxiris membrane or standard AN-69

membrane (Figure 1). Randomization will be performed on the day of admission using online software (EPIDAT 4.2). The intervention will be sustained during 72 continuous hours.

Patients will be randomized to use one of the following membranes (Figure 1):

CRRT using the AN69 Oxiris membrane (intervention group)

CRRT using the standard AN69 membrane (control group)

\*\*\*Given the pandemic lockdown, informed consents for hemodialysis treatment have been collected by phone call. The study protocol and therapeutic options will be presented to the next of kin; in case of approval for study entry, the date and hour will be registered and a formal appointment for signing the informed consent will be scheduled.

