- Effluent delivered dose will be examined using pre-filter BUN and post-filter BUN, according to KDIGO guidelines for acute kidney injury.

Interventions and treatments unrelated to renal support therapies.

- Every patient enrolled in the trial will receive the standard of care according to the attending physician criteria and institutional protocol established in the participant centers.
- In case the patient is receiving antibiotics, the doses administered will remain unadjusted during the 72h period of the study.
- Norepinephrine will be the first-line vasopressor used to maintain MAP between 65-70 mmHg.

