#### 12. Outcomes

Outcomes:

-Primary outcome: to establish the superiority of treatment with the AN69-Oxiris membrane to sustain a similar MAP with a lower requirement of norepinephrine (at least 0.1 micrograms/kg/min) after 72 hours of treatment initiation, in patients with COVID-19 associated AKI requiring CRRT, compared to the usage of a standard AN69 membrane.

-Secondary outcomes:

- To evaluate the effectiveness of the AN69-Oxiris membrane in reducing interleukin serum levels (IL 6, IL 10, and TNF alpha).
- To demonstrate the advantage of the AN69-Oxiris membrane in decreasing 28-day mortality from the start of CRRT.
- To establish the safety of using the AN69-Oxiris membrane in patients with AKI and COVID-19 infection who require CRRT.
- To examine the efficacy of the AN69-Oxiris membrane in reducing the length of ICU stay compared to the use of a conventional membrane (standard AN-69) in critically ill patients with COVID-19 associated AKI and CRRT requirement.

Variables:

Acute kidney injury. Elevation in serum creatinine or decrease in the urinary output according to what is established in the KDIGO guidelines.

Mean arterial pressure. MAP is considered as the perfusion pressure for organs and, a value greater than 60 mmHg is adequate to maintain perfused the organs of an average person. The mean arterial pressure will be registered, either obtained through a peripheral arterial line (calculated from the area under the curve of the arterial pressure graph) or the non-invasive monitor using the oscillometric method.

Furosemide stress test: This term refers to a furosemide bolus of 1 mg/kg (ideal body weight) with subsequent measurement of urine output after 2 hours. It is considered negative when the urine output during this interval is less than 200 ml.

Safety variables:

\* Clotting of the circuit: it is defined as the presence of clots in the circuit lines and/or filter, which condition rise in the transmembrane, pre-filter, or post-filter pressures, warranting a change of the filter.

\* Allergic reaction: the sudden presence of erythema or rash at any time after starting CRRT treatment.

\* Access bleeding: the occurrence of continuous bleeding at the vascular access insertion site any time after the start of CRRT treatment.

\* Catheter-related bloodstream infection: the presence of any microorganism in blood cultures drawn from catheter's lumen.

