### 13. Sample size

The main outcome considered for this study is the mean dose of norepinephrine at 72 hours after CRRT initiation. Previous studies consider that a difference of at least 0.10 micrograms/kg/min without changes in the MAP, in the intervention group compared to the control group, is a meaningful difference to detect.

Standard deviation for norepinephrine: 0.10 micrograms/kg/min.

Type of test: Two-tailed, with a confidence level of 95% and a statistical power of 80%. Solving the following equation to calculate the sample size using the comparison of 2 means method; a total of 34 patients, 17 within each group, is required. If a 10% loss is assumed, the final sample size will be 36 individuals, 18 in the intervention group (AN69 Oxiris membrane), and 18 in the control group (standard AN69 membrane).

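### Section 16 does not name the primary variable, and its between-arm tests leave out baseline norepinephrine dose: a valid plan for the 72-hour dose, but loosely specified and possibly less precise than it could be

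*Combined protocol and SAP*

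**What the plan says.** The combined protocol and SAP describes the primary endpoint in several places.

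- **Sections 7 and 10** share one wording: "Change in norepinephrine requirement by at least 0.1 micrograms / kg / min to maintain similar MAP after initiation of CRRT". The sentence goes on to name the standard AN69 membrane as comparator but gives no time point. Section 10 adds that "MAP measurements will be performed hourly and norepinephrine requirement will be recorded at that time", without saying how hourly records become one value per patient.
- **Section 9** states that the Oxiris membrane "will decrease vasopressor requirement in at least 0.1 micrograms/kilogram/minute to sustain a stable MAP", in contrast with the standard membrane and after 72 hours. It refers to vasopressors, not norepinephrine alone.
- **Section 12** sets out to show that the Oxiris membrane can "sustain a similar MAP with a lower requirement of norepinephrine (at least 0.1 micrograms/kg/min) after 72 hours of treatment initiation", again compared with the standard membrane.
- **Section 13** is the most definite: "The main outcome considered for this study is the mean dose of norepinephrine at 72 hours after CRRT initiation".

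Section 16 mentions neither norepinephrine nor a primary outcome. For continuous variables in general, a Student's t-test "will be used to compare continuous variables between the two groups, in case of a normal distribution", and a Mann-Whitney test is used otherwise, the choice resting on a Kolmogorov-Smirnov test. Baseline appears only in within-group comparisons of baseline with 72 hours. The one adjusted model is the Cox model for mortality, which uses baseline SOFA.

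**The concern.** Section 16 should fix which variable is tested and how. Read alone, it would accept the 72-hour dose, a change from baseline, or some summary of the hourly records. These are different analyses with different power. The trial is open-label, so the choice should not be left until data are in hand. The normality test adds a second choice that depends on the data.

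Baseline dose is also unused where it could help. Section 14 admits patients on any vasopressor dose, so starting doses may vary widely among 36 patients. The within-arm tests do use baseline, but a change within each arm does not compare the membranes. If baseline predicts the 72-hour dose, an unadjusted comparison carries variance that could be removed at almost no cost.

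**Working it through.** **Inputs from the documents.** Section 13: difference 0.10 micrograms/kg/min, SD 0.10, two-sided 5% level, 80% power, 17 per arm before losses. It does not say whether the SD is that of the dose or of a change.

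**Assumptions not in the documents.** SD 0.10 at 72 hours; complete, normal data; a baseline-to-72-hour correlation rho, varied from 0 to 0.7. For the change score, SD 0.10 at baseline as well, unless stated otherwise.

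**1. The plan's own figure.** The unadjusted t-test has SE = 0.10 × √(2/17) = 0.0343 on 32 degrees of freedom. The noncentral t distribution gives 80.7% power. Solving for 80% power gives 16.71, so 17 per arm, which matches Section 13. The 95% interval half-width is 2.037 × 0.0343 = 0.070. (The step from 34 to 36 for losses is a separate matter: 34/0.9 = 37.8.)

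**2. ANCOVA of the 72-hour dose on membrane and baseline dose.** SE = 0.10 × √(1 − rho²) × √[(2/17) × (1 + 1/30)] on 31 degrees of freedom. The factor (1 + 1/30) is the cost of estimating the slope. At rho = 0.5, SE = 0.10 × 0.8660 × √(0.11765 × 1.0333) = 0.0302, and the half-width is 2.040 × 0.0302 = 0.062.

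**3. Change score, if 0.10 is the SD of the dose at both times.** SD of change = 0.10 × √[2(1 − rho)], tested on 32 degrees of freedom.

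| rho | Unadjusted power | ANCOVA power | ANCOVA half-width | Change-score power |
|---|---|---|---|---|
| 0 | 80.7% | 79.3% | 0.071 | 51.6% |
| 0.2 | 80.7% | 80.9% | 0.070 | 60.9% |
| 0.3 | 80.7% | 83.0% | 0.068 | 66.6% |
| 0.5 | 80.7% | 89.4% | 0.062 | 80.7% |
| 0.7 | 80.7% | 97.3% | 0.051 | 95.4% |

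ANCOVA and the unadjusted test have equal power at rho = 0.185. If 0.10 is already the SD of change, the change-score test has 80.7% power at 17 per arm and no correlation is needed.

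**4. Chance imbalance.** With baseline SD 0.10 and 17 per arm, a baseline difference of 0.05 or more in either direction has probability 14.5%. On average, rho × 0.05 of it carries into the unadjusted 72-hour difference: 0.015, 0.025 and 0.035 at rho 0.3, 0.5 and 0.7. At rho 0.5 the shift is 0.025/0.0343 = 0.73 standard errors. This variation is already part of the 0.0343. ANCOVA removes the part explained by baseline, which is why its interval is narrower.

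**The case against.** The strongest reply is that the endpoint is clear when the sections are read together. The full sentences in Sections 7, 9 and 10 name the standard membrane as comparator. Sections 9, 12 and 13 agree on a between-arm contrast at 72 hours, and Section 13 says outright which quantity is the main outcome. No section defines the primary endpoint as change from baseline. This largely stands. A reader might infer that the protocol has contradictory primary endpoints, or that it intends a change score; the documents support neither. What remains is that Sections 7 and 10 omit the time point and say *change*, Section 9 says *vasopressor*, and Section 16 does not point to Section 13.

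The second reply is that baseline adjustment is a preference. The unadjusted test keeps its type I error under randomization with complete, normal data, and the sample size is right for it. The gain from ANCOVA rests on a correlation that the documents do not give. Section 11 says "Norepinephrine will be the first-line vasopressor used to maintain MAP between 65-70 mmHg", and titration to such a target could make the correlation low. All of this stands. It limits the size of the gain but does not remove the case for fixing the analysis in advance, because the most that can be lost is small.

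Third, the fix has its own weak point. Section 11 says "Randomization will be performed on the day of admission using online software (EPIDAT 4.2", whereas Section 17 places randomization before each CRRT treatment begins. If randomization falls on admission, the last dose before it may be some time before CRRT starts and may predict the 72-hour dose less well.

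**Conclusion.** The concern holds as a matter of specification and precision, and the change is recommended. Section 16 should name the primary variable and does not, and its between-arm tests make no use of a baseline dose that the within-arm tests already require.

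Under the stated assumptions, ANCOVA changes power from 80.7% to between 79.3% (rho 0) and 97.3% (rho 0.7). At rho 0.5 it cuts the half-width from 0.070 to 0.062. Below rho of about 0.19 there is no gain. Confidence is medium, because rho is unknown.

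Two stronger readings should be resisted. A reader might infer that chance imbalance makes the planned test invalid. It does not, because that variation is already counted in the standard error. A reader might also infer that the trial is underpowered if change is the endpoint. That follows only if 0.10 is the SD of the dose at both times and rho is below about 0.5; if 0.10 is the SD of change, power is 80.7%.

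**What to change.** 1. State norepinephrine dose at 72 hours as the single primary variable, in the same words, in Sections 7, 9, 10, 12, 13 and 16.
2. In Section 16, make the primary test an ANCOVA of the 72-hour dose on membrane, with the last norepinephrine dose recorded before randomization as the only covariate. Fix this in advance, whatever the normality test shows, and report the adjusted difference with its 95% confidence interval.
3. Name one rank-based sensitivity analysis, for example Quade rank ANCOVA, and always report it.
4. Report within-arm changes from baseline to 72 hours descriptively.
5. Reconcile the timing of randomization in Sections 11 and 17, so that the covariate is clearly measured before randomization.

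The cost is wording in Sections 7, 9 to 13, 16 and 17, plus one pre-randomization norepinephrine dose per patient. Section 16 already needs a baseline value, though Section 10 does not name a pre-randomization reading. No extra patients are needed. The model uses one degree of freedom, and power falls by up to about 1.4 points (80.7% to 79.3%) if rho is near 0. The change does not deal with deaths or missing doses before 72 hours; those need a separate rule.

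### Section 16 names the rank-sum test, which is for independent samples, for the paired baseline v 72 h comparison; the signed-rank test was probably meant

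*Combined protocol and SAP*

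**What the plan says.** Section 16 (Statistical analysis) gives two separate rules for two kinds of comparison.

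- **Between groups:** Student's t-test if the distribution is normal; otherwise, "The Mann-Whitney U-test will be performed for groups with an abnormal distribution".
- **Within a group over time:** the scope of the rule is "The analysis of data inside the same group at different time intervals (baseline vs 72 h". It lists three tests. The non-parametric one for continuous variables is "Wilcoxon sum of ranks"; the others are Student's t-test and McNemar's test. The sentence ends by leaving the choice among the three to what is appropriate.

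The section also sets the threshold: "A p-value <0.05 will be considered significant". The signed-rank test is named nowhere in the document, and the t-test in the within-group rule is not described as paired. Section 13 (Sample size) concerns only the between-group comparison of norepinephrine dose at 72 h. No power or sample size is stated for the within-group comparison.

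**The concern.** Baseline and 72 h values inside one arm are two measurements on the same patients. The rank-sum test pools them as if they came from two unrelated sets of patients. It is equivalent to the Mann-Whitney U-test, which the same paragraph already assigns to the between-group comparison. The closing words of the within-group rule leave a choice only among the tests listed, and none of those is a paired non-parametric test.

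If the text were followed literally, any within-arm change in a non-normal variable would be tested at an error rate other than the stated 5%. Cytokines and norepinephrine dose are plausible candidates, though the document does not say that they will be skewed. With positively correlated pairs, a real change could also be missed.

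**Working it through.** **1. The plan's own figure.** Section 13 takes "a difference of at least 0.10 micrograms/kg/min without changes in the MAP" as the effect and "Standard deviation for norepinephrine: 0.10 micrograms/kg/min", two-sided alpha 0.05 and power 80%.

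- Normal approximation: n per arm = 2 × (1.96 + 0.84)² × (0.10/0.10)² = 15.7, so 16.
- Two-sample t solution: 16.7, so 17 per arm and 34 in total, as stated. Power at 17 per arm is 0.807.

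The stated 34 is therefore reproduced. It uses nothing from the within-group rule.

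**2. Why pairing matters.** Let each time point have SD σ, with n pairs and correlation rho. An independent-samples test on means assumes a variance of 2σ²/n for the difference. The true variance is 2σ²(1 − rho)/n. The large-sample type I error is therefore 2Φ(−1.96/√(1 − rho)):

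- rho 0.3: 1.96/0.837 = 2.34, giving 1.9%
- rho 0.5: 1.96/0.707 = 2.77, giving 0.6%
- rho 0.7: 1.96/0.548 = 3.58, giving 0.03%
- rho −0.3: 1.96/1.140 = 1.72, giving 8.6%

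This describes a test on means and only indicates the direction for ranks. The rank-sum test itself was simulated.

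**3. Simulation.** Inputs from the plan: 18 per arm (section 13) and two-sided alpha 0.05. Assumed, because the documents give none of them: rho, the within-group shift and the distribution. Each cell uses 10,000 normal datasets of 18 pairs and exact tests. The entries are rejection rates, rank-sum v signed-rank.

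| rho | No shift (type I error) | 0.5 SD shift | 1 SD shift |
|---|---|---|---|
| −0.3 | 0.076 v 0.046 | 0.315 v 0.228 | 0.777 v 0.678 |
| 0 | 0.048 v 0.047 | 0.286 v 0.279 | 0.799 v 0.789 |
| 0.3 | 0.023 v 0.047 | 0.253 v 0.373 | 0.840 v 0.909 |
| 0.5 | 0.007 v 0.048 | 0.229 v 0.499 | 0.878 v 0.976 |
| 0.7 | 0.001 v 0.049 | 0.193 v 0.709 | 0.918 v 0.998 |
| 0.9 | 0.000 v 0.044 | 0.143 v 0.992 | 0.976 v 1.000 |

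On the section 13 SD, 1 SD is 0.10 micrograms/kg/min, the same size as the plan's between-group effect.

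Power lost by the rank-sum test:

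- **0.5 SD shift:** none at rho 0; 0.373 − 0.253 = 12 points at 0.3; 0.499 − 0.229 = 27 points at 0.5; 0.709 − 0.193 = 52 points at 0.7.
- **1 SD shift:** the largest loss is 0.976 − 0.878 = 9.8 points, at rho 0.5.

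At rho −0.3 the rank-sum test rejects more often, but only because its type I error is inflated.

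**4. Sensitivity.** Seventeen pairs and lognormal data give the same pattern. With lognormal data and 18 pairs, type I error is 0.007 at rho 0.5 and 0.079 at −0.3, and the 0.5 SD loss at rho 0.7 is 0.650 − 0.189 = 46 points. Type I error at rho 0.7 with normal data varied between 0.1% and 0.2% across separate runs. An unpaired t-test behaves much like the rank-sum test (normal data, 18 pairs: type I error 0.008 at rho 0.5 and 0.081 at −0.3).

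**The case against.** The strongest reply is that this is a naming slip and not a chosen analysis. The authors wrote one rule for comparisons between groups and another for comparisons within a group. The within-group list includes McNemar's test, which is paired. The rank-sum test already appears, as Mann-Whitney, in the between-group rule, so listing it again under another name for a different purpose would be odd. The signed-rank statistic is also a sum of ranks, taken over the differences, so the phrase may simply be loose. Likewise, Student's t-test covers the paired form, so adding the word paired there clarifies and does not correct an error. All of this stands, and it makes signed-rank the likely intention. It does not repair the text, because section 16 is the only analysis section and its list holds no paired non-parametric test.

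It is also fair to say that little depends on this test. The primary outcome (sections 12 and 13) is a between-group comparison, and no power claim or decision rule rests on the within-group tests. With positive correlation the literal error is conservative and would not produce spurious findings of change. This stands too, and it is why the point is minor.

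A reader might infer two further things that the documents do not support. One is that the within-group comparison is badly underpowered in general. That depends on a correlation and a shift that the plan never states: at rho 0 nothing is lost, and at 1 SD the loss is modest. The other is that the plan means to draw treatment effects from within-arm changes and so must declare those tests descriptive. Section 16 does not say this, and the recommendation does not follow from a misnamed test.

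**Conclusion.** The point holds as a wording error in the operative analysis section: the rule for paired data names an independent-samples test, and nothing elsewhere corrects it. Applied literally to correlated pairs, the test does not hold its 5% level. It is conservative when rho is positive and anti-conservative when rho is negative. The loss of power is conditional: from nil to about 50 points for a 0.5 SD shift as rho goes from 0 to 0.7, and about 10 points at most for a 1 SD shift. These sizes rest on assumed correlations, shifts and distributions, and should be read as a range and not as a property of this trial. The primary between-group analysis and the sample size are not affected. Wrong as written; low severity.

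**What to change.** In the within-group sentence of section 16, replace the list of tests with: paired Student's t-test, Wilcoxon signed-rank test, or McNemar's test, as appropriate. The cost is one phrase. The sample size, data collection and primary analysis do not change.
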